9.7.2.3 Secondary objective 2: Incidence of hyponatraemia requiring hospital intensive care

The analysis of hyponatraemia requiring hospital intensive care will be performed analogously to the analysis of incident events of symptomatic hyponatraemia (see 9.7.2.1).

9.7.2.4 Secondary objective 3: Incidence of clinically significant hyponatraemia

Analyses of incident and recurrent events of clinically significant hyponatraemia will be performed analogously to symptomatic hyponatraemia (see 9.7.2.1). Analyses will be performed among patients residing in the regions covered by the Danish National Laboratory Database Research Table (see section 9.4.1.4).

The potential lack of serum sodium measurements, differences in the likelihood of being tested and intensity of testing will be addressed by describing the distribution of risk factors and background characteristics (e.g., relevant demographic and other risk factors such as comorbidities and co-medication) for tested and non-tested patients.

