9.3.2.2 Secondary outcomes

The secondary outcomes for this study are the following events:

1. Hyponatraemia requiring hospital intensive care, defined as a primary or secondary diagnosis of hyponatraemia (ICD-10: E87.1) recorded in an intensive care unit.

This outcome will only be evaluated in Sweden using data collected from the Swedish Intensive Care Registry (SIR; see section 9.4.3.4), as information to distinguish between hospital inpatient care in general and intensive care in particular is not available in the Danish national registries or the German GePaRD (see sections 9.4.1 and 9.4.2, respectively).

Only incident events (first hyponatraemia record from within hospital intensive care during follow-up) will be considered.

2. Clinically significant hyponatraemia, defined as a serum sodium concentration of <130 mmol/L (10).

In addition, hyponatraemia by level of severity will be evaluated, where *mild* hyponatraemia is defined as a serum sodium concentration of 130-<135 mmol/L, *moderate* as a serum sodium concentration of >125-<130 mmol/L, and *severe* as a serum sodium concentration of $\leq 125 \text{ mmol/L}$.

Clinically significant hyponatraemia, including level of severity, will only be assessed in Denmark using data collected from the Danish National Laboratory Database Research Table. The evaluation of this outcome will be restricted to patients residing in the four Danish regions covered by the database (see section 9.4.1.4).

Incident and recurrent events will be considered and analysed separately.

3. All-cause mortality, defined as death from any cause.

This outcome can be evaluated in all data sources: Denmark and Sweden using the national cause of death registries (see sections 9.4.1.5 and 9.4.3.5), and in Germany using the date of death.

4. Major adverse cardiovascular events (MACE (11)), defined as a record of myocardial infarction and stroke, (see Annex 3, Table A3, for a list of diagnosis codes used to define these conditions) recorded in each relevant country data source. In Sweden and Denmark, fatal events of myocardial infarction and stroke are also considered as MACE (as cause of death is available). MACE is a composite endpoint.

In addition to overall MACE events, MACE requiring hospital intensive care defined as defined as a primary or secondary diagnosis of MACE recorded in a hospital intensive care unit will be reported in Sweden.

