9.7.2.1 Primary objective: Incidence of symptomatic hyponatraemia

The incidence rate of the primary outcome reported since index date in the study observation period will be modelled using a Poisson regression model and expressed as number of cases per 1000 patients-years at risk (+95% CI) for the NOCDURNA group and the LUTS contextual cohort, separately. Person-period at risk is defined according to person-time observed from the index date to the first right censoring event. The numerator will comprise of reports of incident symptomatic hyponatraemia during the observation period. The model will be adjusted for relevant strong risk factors (gender, age (<65, 65-74, \geq 75 years). Stratum-specific incidence rates will also be examined. These will be detailed in the SAP.

As in Phase III pivotal clinical trials incidence of hyponatremia is observed to be higher in the first month of treatment with NOCDURNA than in the subsequent months, two separate Poisson regression models will be applied: (1) including only the first month after the index date, and (2) including only subsequent months after the index date (month 2 and onwards). Recurrent events of hyponatremia are not expected in NOCDURNA patients, as treatment should be discontinued after symptomatic hyponatremia has been diagnosed. For both the NOCDURNA and the LUTS group incidence rates (number of events/ 1000 person-years) will be estimated with 95% CIs.

To investigate how the hazard of hyponatremia more precisely develops in time, hazard functions, based on Cox regression models for time to first event since index date (using the same regressors as in the Poisson model) will be plotted as a function of time.

If, however unlikely, recurrent events have been observed, a Cox model for recurrent events may be applied which will be detailed in the SAP.

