10.2.3 Secondary objective 3: Incidence of clinically significant hyponatraemia

Analyses of incident and recurrent events of clinically significant hyponatraemia (<130 mmol/L) will be performed analogously to symptomatic hyponatraemia (see 10.1.2). Analyses will be performed among patients residing in the regions covered by the Danish National Laboratory Database Research Table. There will be 4 analysis stratified by the actual level of sodium concentrations where a *mild* hyponatraemia is a serum sodium concentration above 130 to less than 135 mmol/L, *moderate* is a serum sodium concentration of above 125 to less than 130 mmol/L, and *severe* is a serum sodium concentration of less than or equal to 125 mmol/L and the above specified as clinically significant hyponatraemia (<130 mmol/L)

The potential lack of serum sodium measurements, differences in the likelihood of being tested and intensity of testing will be addressed by describing the distribution of risk factors and background characteristics (e.g., relevant demographic and other risk factors such as comorbidities and co-medication) for tested and non-tested patients. The table shell for this analysis is shown in Table 12 and is repeating the baseline table, but only for the patients from 4 out of 5 Danish regions.

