SOURCE DOCUMENT: DEMOcontra_SWEDEN.SAS GENERATED: 22:53:48 16FEB2021 DB version DEV: ART_03, USER_ID [name]. Calculated on the index date, except for exposure time as defined in this SAP. Only patients from 4 out of 5 Danish regions reporting to the National Lab database.

Table 12. Secondary objective 1. Demographic and health characteristics in *Denmark* stratified according to patients with sodium measurements and patients without sodium measurements.

Repeat table shell from Table 10 and stratify according to patient with and without measurements.

Figures of continuous variables.

Figure 7. Secondary objective 1. A Boxplot of age divided by treatment group in *country*.

[figure not shown]

Figure 8. Secondary objective 1. A symmetry plot of age divided by treatment group in country (only one group is shown).

[figure not shown]

Figure 9. Secondary objective 1. A normal quantile plots of age divided by treatment group (Nocdurna ® and LUTS) in *country* (only one group is shown).

[figure not shown]

Figure 10. Secondary objective 1. A normal probability plots of age divided by treatment group in *country* (only one group is shown).

[figure not shown]

Figure 11. Secondary objective 1. A Boxplot of exposure time divided by treatment group in *country*.

Repeat Figure 7 with exposure time instead of age.

Figure 12. Secondary objective 1. A symmetry plot of exposure time divided by treatment group in country.

Repeat Figure 8 with exposure time instead of age.

Figure 13. Secondary objective 1. A normal quantile plots of exposure time divided by treatment group (Nocdurna ® and LUTS) in *country*.

Repeat Figure 9 with exposure time instead of age.

Figure 14. Secondary objective 1. A normal probability plots of exposure time divided by treatment group in *country*.

Repeat Figure 10 with exposure time instead of age.

Table 13. Secondary objective 2. Incidence of hyponatraemia requiring hospital intensive care (ICU) in *Sweden*.

Repeat Table 9 with changed outcome

Figure 15. Secondary objective 2. A Cox regression showing time to first event hyponatraemia requiring hospital intensive care (ICU) stratified by patient group and age class in Sweden.

Table 14. Secondary objective 3. Incidence of clinically significant hyponatraemia (lab value) in *Denmark*: serum sodium concentration <130 mmol/L

Repeat Table 9 with changed outcome

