>=75 years compared with <65 y	XX.XX	(XX.XX, XX.XX)	0.xxxx
Males compared with females	XX.XX	(XX.XX, XX.XX)	0.xxxx
Scale – one value for each model	XX.XX		
Events after first month and onwards,			
all sub-populations			
Nocdurna ® compared with LUTS	XX.XX	(xx.xx, xx.xx)	0.xxxx
65-74 years compared with <65 y	XX.XX	(XX.XX, XX.XX)	0.xxxx
>=75 years compared with <65 y	XX.XX	(XX.XX, XX.XX)	0.xxxx
Males compared with females	XX.XX	(XX.XX, XX.XX)	0.xxxx
Scale – one value for each model	XX.XX	,	

Table 29. Secondary objective 7. Comparative analyses for Incidence of symptomatic hyponatraemia in *country*.

For incidence rates see **Table 9**. IRR= Incidence Rate Ratio: Ratio of IR to that of Control, where the controls are LUTS, <65 y age and females as indicated in the rows.

SOURCE DOCUMENT: Compare_prim.SAS GENERATED: 22:53:48 16SEP2021 DB version DEV: ART_03, USER_ID [name].

Table 30. Secondary objective 7. Comparative analyses for incidence of hyponatraemia requiring hospital intensive care in *Sweden*.

Repeat Table 29, with incidence of hyponatraemia requiring hospital intensive care in *Sweden* as outcome.

Table 31. Secondary objective 7. Comparative analyses for incidence of clinically significant hyponatraemia in *Denmark*.

Repeat Table 29, with changed for incidence of clinically significant hyponatraemia in *Denmark* as outcome.

Table 32. Secondary objective 7. Comparative analyses for all-cause mortality in *country*.

Repeat Table 29, with all-cause mortality as outcome.

Table 33. Secondary objective 7. Comparative analyses for incidence of major cardiovascular events in *country*.

Repeat Table 29, with for incidence of major cardiovascular events as outcome.

Table 34. Secondary objective 7. Comparative analyses for incidence of major venous thromboembolic events in *country*.

Repeat Table 29, with incidence of major venous thromboembolic events as outcome.

Table 35. Secondary objective 7. Comparative analyses for incidence of major venous thromboembolic events in *country*.

Repeat Table 29, with incidence of major venous thromboembolic events as outcome.

Table 36. Secondary objective 7. Comparative analyses for incidence of acute exacerbation of congestive heart failure in *country*.

Repeat Table 29, with incidence of acute exacerbation of congestive heart failure as outcome.

Table 37. Secondary objective 8. Cardiovascular and thromboembolic events resulting in treatment withdrawal in *Sweden*. Nocdurna ® patients only.

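### Describing tested and non-tested patients does not correct the rates or rate ratio of sodium <130 mmol/L for unequal testing; testing frequency by cohort and window, a labelled tested-only sensitivity analysis and a caveat are needed

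*Protocol*

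**What the plan says.** The outcome is a laboratory value (Protocol 9.3.2.2) taken from the Danish laboratory database. Protocol 9.7.2.4 analyses it in the same way as the primary outcome, and SAP 10.2.3 repeats this: "Analyses will be performed among patients residing in the regions covered by the Danish National Laboratory Database Research Table". Being tested is not a condition of entry. Under Protocol 9.7.2.1, "Person-period at risk is defined according to person-time observed from the index date to the first right censoring event", and the named adjusters are gender and age class. Protocol 9.7.2.9 adds treatment group to the same Poisson model for secondary outcomes where possible, and SAP Table 31 is the shell for the resulting rate ratio.

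Protocol 9.7.2.4 recognises that sodium may not be measured in everyone. Its stated handling is that "differences in the likelihood of being tested and intensity of testing will be addressed by describing the distribution of risk factors" and background characteristics in tested and non-tested patients. The SAP shell for this, Table 12, is an instruction to repeat Table 10 and "stratify according to patient with and without measurements".

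The sensitivity analyses in Protocol 9.7.3 concern the construction of treatment episodes. Protocol 9.9.1 discusses differential misclassification of the diagnosis code only, and 9.9.2 notes only that laboratory data cover part of Denmark.

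**The concern.** A sodium value below 130 mmol/L can be recorded only if blood was drawn. A patient who is never tested adds person-time to the denominator and cannot add an event to the numerator. If the two cohorts are tested to different degrees, their rates are understated to different degrees and the rate ratio mixes drug effect with testing practice. The same applies to the first-month versus later comparison that 9.7.2.1 calls for, if testing is more frequent in one window than in the other.

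Comparing the characteristics of tested and non-tested patients may show who gets tested, but it leaves every rate, rate ratio and hazard curve unchanged. A simple tested/non-tested split also cannot show intensity, which is one of the two differences the protocol says it will address. This is the study's only laboratory-based hyponatraemia outcome, so a reader will want to know how far its comparison can be relied on.

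**Working it through.** **Inputs.** Danish NOCDURNA patients: 1,830 (Protocol 9.5.3). Laboratory coverage: 4.4 million of 5.7 million residents (Protocol 9.4.1.4 and 9.4.1.2). Phase 3 frequency of sodium below 130 mmol/L: 2-3% (Protocol 7), used only for illustration. The proportion tested in each cohort is not given anywhere and is assumed below.

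**The plan's own figure.** 82,260 lyophilisates / (360 days x 0.5) = 457 patients per year; x 4 years = 1,828, against 1,830 stated. It reproduces.

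**Expected events.** 1,830 x 4.4/5.7 = about 1,413 covered patients. At 2-3% this is 28 to 42 true events in the NOCDURNA cohort.

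**Effect of unequal testing.** Let p be the proportion tested and assume that testing is unrelated to sodium. Then

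- observed rate = true rate x p
- observed IRR = true IRR x p(NOCDURNA) / p(LUTS)

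The same holds within each age and gender stratum, so adjustment for those two factors removes only the part of the testing difference that they explain. With the two time windows in place of the two cohorts, the formula gives the distortion of the first-month versus later ratio.

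With true IRR = 1 and 2.5% risk, Poisson counts were simulated 200,000 times to find how often a 95% Wald interval for the IRR excludes 1:

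| Tested, NOCDURNA / LUTS (assumed) | Observed IRR | Interval excludes 1, cohorts 1:1 | Interval excludes 1, cohorts 1:50 |
|---|---|---|---|
| 50% / 50% | 1.0 | 5% | 5% |
| 60% / 50% | 1.2 | 8% | 15% |
| 80% / 50% | 1.6 | 33% | 65% |
| 40% / 80% | 0.5 | 58% | 82% |

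Both cohort ratios are shown because the documents differ. Protocol 8 speaks of a LUTS cohort of similar size, whereas SAP 3.1.2.1 expects about 300,000 LUTS patients.

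**Restriction to tested patients.** Numerator and denominator both scale with p, so p cancels and the expected IRR returns to 1. This depends on the same condition, that testing is unrelated to sodium.

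**What Table 12 would show.** Table 10 has NOCDURNA and LUTS columns and an N row. Repeating it for tested and non-tested patients gives a crude tested proportion for each cohort. It has no row for the number or timing of tests.

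**The case against.** The protocol does not overlook the problem: it names both likelihood and intensity of testing. Protocol 9.7 allows analyses to be revised and detailed in the SAP. The objective asks for separate rates, and the comparison is made only where possible. Table 12 already yields a crude tested proportion. All of this stands and limits the point, but it does not rescue the remedy, because the protocol itself fixes description as the way the difference is addressed, and the SAP text repeats it.

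A reader might infer that NOCDURNA patients are tested more, so that the rate ratio is inflated. Hyponatraemia is a stated safety concern for NOCDURNA, and one cited reference has sodium monitoring in its title. That makes unequal testing plausible, but the documents give no testing frequency for either cohort and do not say which is tested more. Neither the direction nor a likely size can be claimed.

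The simple formula also needs testing to be unrelated to sodium. If tests are prompted by symptoms, untested patients hold fewer missed events and the observed ratio lies closer to the true one.

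The tested-only analysis has its own bias. It conditions on a test after the index date. If the less-tested cohort is tested mainly when ill, its rate is raised and the ratio is biased the other way. Events per 1,000 tests are weighted towards patients who are tested repeatedly. Neither can replace the all-patient rate.

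**Conclusion.** The point holds as a cheap improvement to a secondary, Denmark-only outcome. The stated handling of unequal testing changes no estimate. The all-patient rate is a rate of detected events, hence a lower bound on the true rate in each cohort, and the rate ratio may partly reflect testing. The possible size runs in both directions: 1.6 at an assumed 80% versus 50% tested and 0.5 at 40% versus 80%, with a true ratio of 1 and testing unrelated to sodium, and nearer to 1 if testing follows symptoms. These are illustrations and not estimates of the bias in this study.

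Two stronger conclusions are not supported. The plan does not leave the reader with no information on testing, since Table 12 gives a crude proportion. And nothing in 9.7.2.4 affects the primary outcome, which rests on recorded diagnoses.

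**What to change.** In Protocol 9.7.2.4, and correspondingly in SAP 10.2.3:

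- Report, by cohort and by window (first 30 days, later), the proportion of patients with at least one post-index sodium test and the number of tests per person-year.
- Add a sensitivity analysis of the rates and the rate ratio restricted to tested patients, labelled as subject to selection and read beside the all-patient result.
- State that the all-patient rate is a rate of detected events and a lower bound, and that the rate ratio may reflect testing differences.
- Replace the statement that testing differences are addressed by description with a reference to these analyses.
- Add differential testing to the limitations in Protocol 9.9.

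Events per 1,000 tests may be shown descriptively only.

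The cost is a few extra table rows and one rerun of the existing analysis on Danish laboratory data that the study already plans to use. The downside is that the tested subgroup is selected, so the sensitivity analysis indicates how much testing could matter and does not give a corrected estimate.

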9.7.2.5 Secondary objective 4: All-cause mortality

The analysis of all-cause mortality will be performed analogously to that of incident events of symptomatic hyponatraemia, from the index date (see 9.7.2.1).

9.7.2.6 Secondary objective 5a: Incidence of major cardiovascular events

The analysis of incident MACE will be performed analogously to that of incident events of symptomatic hyponatraemia (see 9.7.2.1), from index date. Fatal and non-fatal MACE and VTE events will be assessed separately.

In addition, time to events requiring hospital intensive care and cardiovascular death, respectively, will be described for patients with an incident diagnosis of MACE in the study time period. Events requiring hospital intensive care will be defined as a primary or secondary diagnosis of MACE recorded in a hospital intensive care unit (reported in Sweden only). Cardiovascular death is defined as a relevant diagnosis recorded as the underlying or contributing cause of death (reported for Sweden and Denmark).

9.7.2.7 Secondary objective 5b: Incidence of major venous thromboembolic events

The analysis of incident VTE events will be performed analogously to that of incident events of symptomatic hyponatraemia (see 9.7.2.1), from index date.

Similar to MACE, time to events requiring hospital intensive care and death from a VTE event, respectively, will be described for patients with an incident diagnosis of VTE in the study time period.

9.7.2.8 Secondary objective 6: Incidence of acute exacerbation of congestive heart failure

The analysis of this outcome will be performed analogously to that of incident events of symptomatic hyponatraemia (see 9.7.2.1).

9.7.2.9 Secondary objective 7: Comparative analyses

Where possible, for the comparative analyses of primary and secondary outcomes of interest, the same analyses (Poisson regression) as in Section 9.7.2.1 will be applied but now with treatment group (NOCDURNA/LUTS) as an additional factor. To investigate if the incidence rate ratio (IRR) for the Poisson regression of NOCDURNA to LUTS depend on confounders, treatment by confounder interaction terms will be investigated to see if and to what extent (quantitative or qualitative) the IRR depend on the respective confounding factor. These multiple regression methods will be detailed in the SAP.

9.7.2.10 Secondary objective 8: Cardiovascular and thromboembolic events of interest resulting in treatment withdrawal

The analysis of this outcome will be performed analogous to that of incident events of symptomatic hyponatraemia (see 9.7.2.1) for NOCDURNA only. MACE and VTE events considered to be associated with treatment cessation will be those events for which the event date occurs within 14 days prior to the treatment cessation date (see section 9.3.1). Serious MACE and VTE events will be defined as a primary or secondary diagnosis of MACE or VTE recorded in a hospital intensive care unit. This can be only evaluated in Sweden.

9.7.2.11 Secondary objective 9: Incidence rate in patients stratified according to the label by proxy

The analysis of this outcome will be performed analogous to that of incident events of symptomatic hyponatraemia (see 9.7.2.1) for NOCDURNA only. The subgroup of patients adhering to the label will be defined by a proxy based on diagnosis and contra-indications as available in the respective registries. This will be detailed in the statistical analysis plan

In this analysis the outcomes specified as the primary objective and secondary objectives 1-6 will be repeated for the NOCDURNA only patients. The subgroup of patients adhering to the label will be defined by a proxy based on diagnosis and contra-indications as available in the respective registries based on the information in the SmPC. Two population will be created for all NOCDURNA patients, one with contra-indication for treatment and another as the remaining NOCDURNA patients without contra-indication. The contra-indication for treatment must be present before the first recorded dispensation of NOCDURNA. This approach will be detailed in the statistical analysis plan

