7. In addition, a subgroup analysis of all patients adhering to the label as assessed by the proxy based on diagnosis and contra-indications (as available) will be conducted.

8.

- 9. Estimate the incidence rate of primary and secondary outcomes of interest between patients treated with NOCDURNA compared to a population of LUTS patients adjusted for confounding factors, by country where data available.
- 10. Estimate the incidence rate of cardiovascular and thromboembolic events of interest resulting in treatment withdrawal of NOCDURNA.

All secondary objectives will be evaluated in the overall population and among subgroups of interest (including elderly, aged ≥65 years).

9 **RESEARCH METHODS**

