9.9.3 Definition of the NOCDURNA cohort

There is no specific diagnosis code for idiopathic nocturnal polyuria, which is the indication for NOCDURNA. Instead the present study will include all patients that are treated with NOCDURNA (irrespective of underlying disease). This approach will give a broad and comprehensive assessment of the safety of NOCDURNA. All study objectives will, however, be evaluated among patients with a diagnosis of polyuria at the time of their first NOCDURNA prescription.

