The analysis will first calculate the treatment cessation date and then within a 14 days window before the treatment cessation date examine if there is a MACE or VTE event reported from the intensive care register.

Secondary objective 9: Incidence rate in patients stratified according to the label by proxy

The analysis of this outcome will be performed analogous to that of incident events of symptomatic hyponatraemia but only for the Nocdurna ® patients. The subgroup of patients adhering to the label will be defined by a proxy based on diagnosis and contra-indications as stated in the SmPC and the data for classifying the patients according to contraindications should be done as available in the respective registries.

Two population will be created for all Nocdurna ® patients, one with contra-indication for treatment and another as the remaining Nocdurna ® patients without contra-indication. The contra-indication for treatment must be present before the first recorded dispensation of Nocdurna ®.

The following diseases will be considered as contraindications for the prescription of Nocdurna ®, if the diseases are found before or at the index date.

- History of hyponatraemia
- Polydipsia
- Congestive heart failure (chronic)
- Kidney disease (chronic kidney disease stage 3 and over)
- Syndrome of inappropriate antidiuretic hormone secretion (SIADH)

The ICD 10 codes for the above can be found in the given in Table 71. The analysis will be done by using the SAS macro 'Nocdurna_mac' and changing the macro call with 'compare=Off label' and creating a class group with 'Off label' instead of 'LUTS' as described in section 16.1

The analysis of the sub-population will be done for the primary objective and for secondary objective 2, 3, 4, 5a, 5b and 6.

Observe that this analysis is changed from the description in the study protocol.

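### Objective 9 announces label adherence as diagnosis plus contraindications but splits on contraindications alone, and the polyuria-diagnosis evaluation promised in section 9.9.3 is missing from the analysis sections

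*Protocol*

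**What the plan says.** The label-adherence analysis is item 7 of the secondary objectives in protocol section 8 and secondary objective 9 in section 9.7.2.11. Both places name two elements. Section 8 announces "a subgroup analysis of all patients adhering to the label as assessed by the proxy based on diagnosis and contra-indications (as available". Section 9.7.2.11 says that the subgroup "will be defined by a proxy based on diagnosis and contra-indications as available in the respective registries based on the information in the SmPC".

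The construction follows in the same section: "Two population will be created for all NOCDURNA patients, one with contra-indication for treatment and another as the remaining NOCDURNA patients without contra-indication". The only timing rule concerns the contraindication: "The contra-indication for treatment must be present before the first recorded dispensation of NOCDURNA".

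Section 9.9.3, among the limitations, explains that the indication has no specific diagnosis code and describes the cohort: "Instead the present study will include all patients that are treated with NOCDURNA (irrespective of underlying disease". It then offers a counterweight: "All study objectives will, however, be evaluated among patients with a diagnosis of polyuria at the time of their first NOCDURNA prescription".

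The SAP text keeps the one-element split. Its objective 9 opens the classification with "The following diseases will be considered as contraindications for the prescription of Nocdurna" and lists five conditions, none of them an indication. SAP section 10.1.2 describes the two resulting groups as patients who do, and patients who do not, use the drug as the product information intends.

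**The concern.** According to protocol section 7, the member states required the study in order to evaluate safety concerns and to collect long-term data in patients aged 65 or over who are treated according to the approved product information. Objective 9 is the analysis that comes closest to isolating such use. Label use has two sides: a patient has the indication, and a patient has no contraindication. The split measures only the second.

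The 9.9.3 evaluation is the one place where the protocol undertakes to look at the indication side in the outcome analyses. If it is not carried into the analysis sections, the country teams have no instruction to run it, and the final report could present the no-contraindication rate as the rate under label use.

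**Working it through.** There is no sample size, power or event figure to reproduce. The check sets the passages side by side.

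1. **Announced definition against construction.** Sections 8 and 9.7.2.11 name diagnosis and contraindications. The construction in 9.7.2.11 forms one group with a contraindication and a second group of everyone else. These groups are exhaustive, so no third cell exists in which a diagnosis condition could act. The timing rule covers contraindications only.

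2. **Could diagnosis simply mean the codes that identify contraindications?** The wording lists two elements. Section 9.3.3 separately collects treatment indication, defined as the diagnosis that precedes the NOCDURNA prescription. The two-element reading is the natural one.

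3. **Where is the 9.9.3 population?**
   - Section 9.2.5 lists the elderly and the contraindication groups. Polyuria is absent.
   - Sections 9.7.2.1 to 9.7.2.11, 9.7.3 and 9.7.4 contain no analysis restricted to, or stratified by, a polyuria diagnosis.
   - Annex 3 Table A2 (subpopulation codes) does not list R35. R35 appears only in Table A4, as a covariate.
   - In the SAP text, R35 appears in baseline tables. No outcome table shell is restricted to or stratified by it.

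4. **Who falls in the no-contraindication group?** Cohort entry ignores underlying disease. Every NOCDURNA user without a listed contraindication is therefore included, with or without a recorded supporting diagnosis.

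5. **Can the effect be sized?** Let s be the share of the no-contraindication group without a supporting record, and r the ratio of their event rate to that of patients with one. With s as a share of person-time, the reported rate relative to the rate in patients with a record is 1 + s(r − 1). The documents give neither s nor r. Assumed values, chosen only to show that the sign is open:
   - s = 0.2 to 0.8, r = 1.5: 1 + 0.2 × 0.5 = 1.10 to 1 + 0.8 × 0.5 = 1.40.
   - s = 0.2 to 0.8, r = 0.67: 1 − 0.2 × 0.33 = 0.934 to 1 − 0.8 × 0.33 = 0.736.

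   These are not estimates. They compare patients with and without a record, not patients with and without the indication.

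**The case against.** The strongest reply is that the protocol leaves the detail to the SAP: 9.7.2.11 says so for this subgroup, and 9.7 allows the analyses to be revised there. That would answer a missing code list or look-back window. It does not answer a two-group partition already fixed in the protocol that leaves out an announced element. The SAP text does not repair it either. It says that objective 9 differs from the protocol, but its section 13 explains only the shorter contraindication list. Neither the diagnosis element nor the polyuria evaluation is mentioned.

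Second, part of the information is already planned. SAP Table 10 shows R35 and E23.2 by cohort, Table 11 repeats that structure for NOCDURNA patients with and without contraindications, and Table 59 shows both codes by country. Tables 11 and 38 to 44 are already titled by contraindication. This stands. What is missing is outcome rates by R35 status, and consistent naming in the text.

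Third, the diagnosis proxy is weak. Section 9.9.3 says there is no specific code, section 9.9.2 says that the Danish and Swedish patient registries lack primary-care diagnoses, and the protocol promises only what is available. This also stands and limits what an R35 stratum can show. The protocol does not, however, give it as a reason to drop the diagnosis element, and it promises the polyuria evaluation in the same section that admits the problem.

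A reader might go further and infer that off-indication users are being counted as label-adherent. The documents do not support that. A patient without an R35 record may be correctly treated, and a patient with one need not have idiopathic nocturnal polyuria.

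**Conclusion.** The contradiction within 9.7.2.11 is real, and the 9.9.3 commitment has no counterpart in the sections that define populations and analyses. As built, objective 9 can compare NOCDURNA patients with and without a recorded contraindication. It cannot deliver a rate under label use. The primary estimate in all NOCDURNA users is unaffected.

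Size and direction are unknown. A reader might infer that the no-contraindication rate is biased by a given percentage or in a given direction. Nothing in the documents anchors either.

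A reader might also infer that patients with diabetes insipidus (E23.2) belong outside the label-adherent group. The documents list E23.2 as a covariate, not as a contraindication, and a recorded code does not show why NOCDURNA was dispensed. Entry is limited to the NOCDURNA brand at its two strengths, use of vasopressin analogues in the preceding six months excludes, and dispensing of another desmopressin drug censors. These rules narrow the scope for such cases without settling it.

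**What to change.** 1. Add the polyuria-diagnosis (R35) population promised in 9.9.3 to sections 9.2.5 and 9.7.2.11, and R35 to Table A2, with the time window stated.
2. Report at least the primary outcome among NOCDURNA patients without contraindication, split by presence or absence of an R35 record at or before index, by country. If only the primary outcome is reported this way, narrow the sentence in 9.9.3, which now covers all objectives.
3. State beside the results that absence of a code does not show off-indication use, because the code is non-specific and the Danish and Swedish registers lack primary-care diagnoses.
4. Call the existing split *with/without recorded contraindication* throughout. Remove the label-adherence name from it in the protocol and the intended-use description in SAP section 10.1.2.
5. Keep E23.2 descriptive only.

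The cost is one further stratum from a code already in Table A4 and in the SAP baseline tables. The downside is that the R35 stratum may be small and is an imperfect proxy, especially in Denmark and Sweden. If the sponsor decides that it would not be informative, the 9.9.3 promise and the diagnosis element of the definition should be withdrawn explicitly, with the reason given.
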